Official Title: Telephone-Facilitated Insomnia Treatment in Primary Care for OEF/OIF/OND
Veterans

NCT Number: 02571452

Document Date: 1/2/2020

Study Protocol

Background: Insomnia is a growing public health concern and is associated with a number of negative health outcomes and psychosocial impairment.¹⁻³ Sleep disturbances are highly prevalent in military personnel returning from recent deployments; impact psychosocial functioning, cognitive functioning, productivity, and quality of life; and are one of the most common reasons that veterans seek treatment.⁴⁻⁵ While there have been prior trials examining the efficacy of insomnia treatment among veterans, much of this research has focused on sleep medications.⁶⁻⁸ However, participants report a preference for behavioral interventions over sleep medications.⁹⁻¹⁰ Although empirically-supported behavioral interventions for insomnia are typically offered to veterans through mental health clinics (e.g., Cognitive Behavioral Therapy for Insomnia [CBT-I]; generally lasting 6-8 sessions)¹¹, most veterans who need these treatments report a large number of barriers to seeking treatment, including the stigma associated with mental health care and number of sessions required for treatment completion.¹²⁻¹⁴ Thus, many veterans who could benefit from these treatments do not get needed care.

Brief Behavioral Treatment for Insomnia (BBTI) is a four-session behavioral insomnia treatment that consists of two in-person and two telephone sessions. Research indicates BBTI provides significant improvement in sleep, mood, and health measures for elderly primary care patients in community clinics.¹⁵ A preliminary study of a small sample of young veterans (n=40) suggests BBTI improves insomnia outcomes, but further research in a larger trial was recommended.¹⁶

Objectives: The first aim of the current project was to evaluate the efficacy of BBTI in a large veteran sample that was diverse in age. The primary outcome measure for the study assessed work and social functioning (Work and Social Adjustment Scale; WSAS)¹⁷ and the secondary outcome measure examined sleep-related outcomes (Insomnia Severity Index; ISI).¹⁸ The second aim was to determine whether BBTI gains in psychosocial functioning and insomnia severity were durable.

Design: The study was a parallel design, randomized, controlled trial (RCT) to test the efficacy of BBTI, compared to a progressive muscle relaxation training (PMRT) control condition. PMRT was matched for therapist time with two in-person and two phone sessions and has been used as a comparison treatment in prior insomnia research.¹⁹⁻²² To evaluate the durability of BBTI gains, veterans randomized to BBTI also participated in a six-month follow-up visit to complete primary and secondary outcome measures.

Methods: Post-deployment veterans between 18-75 years of age were recruited through advertisements, referrals from local VA research studies or VA clinicians, and through direct mailings to veterans who had either received primary care at VA hospitals in the San Francisco Bay area or lived within a 40-mile radius of San Francisco. Interested veterans participated in an initial brief phone screen to ensure they met preliminary criteria. Veterans were invited to the San Francisco VA Medical Center, told about the study in detail, and completed consent procedures. Prior to randomization, participants completed demographic and medical history questionnaires, and a clinician-administered, mental health diagnostic interview (Structured Clinical Interview for DSM 5 [SCID-5]²³ and Clinician Administered PTSD Scale [CAPS-5])²⁴). These diagnostic interviews were repeated at post-treatment.

Ninety-three veterans with Insomnia Disorder were randomized 1:1 to either the BBTI or PMRT control arm within strata defined by age (18-50 vs. 51-75) and therapist assignment (one of

three therapists) within randomly generated block sizes (4, 6, and 8). Both BBTI and PMRT consisted of four treatment sessions (one 60-minute and one 30 minute in-person session, and two 20-minute phone-based sessions). Primary and secondary self-report outcome measures of psychosocial functioning (WSAS) and insomnia severity (ISI) were completed at baseline, mid-treatment and post-treatment (and at six-month follow-up for the BBTI group only).

Statistical Analysis & Results: The primary and secondary outcome variables were analyzed with separate linear mixed effects models, with participants as a random effect and time point, age group, and therapist as fixed factors. For each analysis, baseline values of the outcome variables were included as a covariate, with the first outcome time point being mid-treatment. Time point was treated as a categorical variable to avoid assumptions of linearity or any other functional form for outcome variables over time. Residuals from models were approximately normally distributed, so no transformations were considered. To address the first aim, treatment effects were defined as the difference between treatment arms at the post-treatment time point, after adjusting for baseline and stratification variables (age group and therapist). For the second aim, treatment durability effects were defined as the difference between post-treatment and six-month follow-up outcomes for the BBTI group, after adjusting for baseline and stratification variables (age group and therapist).

Two participants were not included in analyses because they were pilot participants that did not meet all eligibility criteria. Thus, ninety-one participants were included in the intent-to-treat analyses. Two of these 91 participants were withdrawn by staff during treatment or 6-month follow-up due to no longer meeting eligibility criteria, and therefore, did not have complete data. Further, five of the 46 individuals that completed BBTI treatment were lost to follow-up. The five BBTI completers at six-month follow-up (11%) could possibly bias comparisons between end of treatment and follow-up, although this loss to follow-up rate is also very low.

Participants ranged in age from 24 to 74 years (M=49 years); 80% were male (n=73), 19% were female (n=17) and 1% were transgender (n=1); 47% were Caucasian (n=43), 19% were Asian (n=17), 13% were Black/African American (n=13), 10% were Latino/Hispanic (n=9), 8% identified as multiracial or other (n=7) and 3% were Native American/Pacific Islander (n=3). Of the 91 participants, 43% served in the Army, 22% served in the Air Force, 21% served in the Navy, 16% served in the Marine Corps, and 6% served in one of the other service branches. Participants randomized to BBTI (n=46) reported significant improvement on measures of psychosocial functioning ($p=.02$) and insomnia severity ($p<.001$). Furthermore, participants in the BBTI arm reported no significant change in symptoms from post-treatment to six-month follow-up for psychosocial functioning ($p=.57$) and insomnia severity ($p=.17$), indicating that BBTI treatment gains were maintained during the follow-up period.

References:

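### Two non-significant tests do not show that BBTI gains lasted: the second aim needs the change, its direction and its confidence interval

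*Combined protocol and SAP*

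**What the plan says.** The Objectives section of the combined protocol and SAP sets the question: "The second aim was to determine whether BBTI gains in psychosocial functioning and insomnia severity were durable". The Design section gives the purpose of the late visit: "To evaluate the durability of BBTI gains, veterans randomized to BBTI also participated in a six-month follow-up visit". PMRT participants have no six-month assessment, so the comparison is within one arm.

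Statistical Analysis & Results defines the effect measure: "treatment durability effects were defined as the difference between post-treatment and six-month follow-up outcomes for the BBTI group", adjusted for baseline and the stratification variables. It gives no margin, threshold or other rule for when gains count as durable. On attrition it reports that "five of the 46 individuals that completed BBTI treatment were lost to follow-up", puts this at 11%, and concedes that the loss might bias the comparison while calling the rate very low.

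The results paragraph says that "participants in the BBTI arm reported no significant change in symptoms from post-treatment to six-month follow-up", with p=.57 for the WSAS and p=.17 for the ISI, and concludes from this: "indicating that BBTI treatment gains were maintained during the follow-up period". No estimate, sign, standard error or interval accompanies the p-values.

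**The concern.** The contrast itself is a reasonable way to examine durability. The problem is the step from the test to the conclusion. Each test takes no change as its null hypothesis, so a large p-value means only that the data do not contradict no change. They may not contradict a meaningful relapse either. Read this way, a smaller or noisier study would find maintenance more easily.

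This sentence is the whole reported answer to one of the trial's two aims. A reader would take it as evidence that a four-session treatment holds for six months. The figures that would support or undermine that reading are not reported.

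**Working it through.** **Inputs.** From Statistical Analysis & Results: 46 BBTI completers, 5 lost to follow-up, p=.57 (WSAS) and p=.17 (ISI). Assumed, because not stated: two-sided tests at 5%. Approximation: a paired t-test stands in for the mixed-model contrast, whose standard error is not reported. Results are therefore in units of the SD of within-person change (s).

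**Reproducing the stated figure.** 5/46 = 10.9%, which agrees with the stated 11%. That leaves 46 − 5 = 41 people.

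**What the p-values leave open.** With n=41 and 40 degrees of freedom, the critical value is 2.021 and √41 = 6.403. Each p-value gives |t|, and the largest loss inside the 95% interval is

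- (2.021 + |t|)/√41 if the observed shift was a worsening,
- (2.021 − |t|)/√41 if it was an improvement.

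| Scale | p | abs(t) | Observed shift, either direction | Largest loss not excluded, if worsening | Largest loss not excluded, if improvement |
|---|---|---|---|---|---|
| WSAS | .57 | 0.573 | 0.573/6.403 = 0.09 s | 2.594/6.403 = 0.405 s | 1.448/6.403 = 0.226 s |
| ISI | .17 | 1.397 | 1.397/6.403 = 0.22 s | 3.418/6.403 = 0.534 s | 0.624/6.403 = 0.097 s |

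For the ISI the unreported direction moves the limit more than fivefold (0.534/0.097 = 5.5).

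**Sensitivity.**

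- *Effective sample size.* The figure of 41 is approximate. Two participants were "withdrawn by staff during treatment or 6-month follow-up due to no longer meeting eligibility criteria", their arm is not stated, and a mixed model can use data from all 46. With n=39 the limits (worsening/improvement) are 0.416/0.232 s for the WSAS and 0.548/0.100 s for the ISI. With n=46 they are 0.381/0.213 s and 0.503/0.091 s.
- *Degrees of freedom.* Normal quantiles at n=41 give 0.395/0.217 s and 0.520/0.092 s.
- *Rounding of the p-values.* Taking .565 to .575 and .165 to .175 moves the limits by at most 0.003 s.

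**How readily a real loss would go undetected.** For an illustrative true loss of 0.30 s, noncentral-t power at n=41 is 0.466, so the test would be non-significant about 53% of the time (55% at n=39, 49% at n=46). The same loss would be non-significant about 75% of the time with 20 people and about 20% with 90. At n=41, 80% power needs a true change of about 0.45 s (0.46 at n=39, 0.42 at n=46).

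**On the scales themselves.** The SD of change is not reported. For an assumed SD of 4 to 10 points, the n=41 limits are 1.6 to 4.1 points (WSAS) and 2.1 to 5.3 points (ISI) if the shift was a worsening, and 0.9 to 2.3 and 0.4 to 1.0 points if an improvement. The share of the treatment gain this represents cannot be worked out, because the gain is not reported either.

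**The case against.** Four points can be made for the document.

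- *The unknown direction cuts both ways.* If scores improved after treatment, losses above 0.10 s (ISI) and 0.23 s (WSAS) are already excluded, which might well count as maintenance. This stands, and it is why durability cannot be called refuted. It does not support the sentence as written, because the reader is not told the direction.
- *This is a short retrospective summary, and the first aim is also reported by p-values alone.* That is true, so missing estimates are not peculiar to the second aim. The difference is that here a claim of no meaningful change rests on non-significance, which a p-value alone cannot support. A fuller report elsewhere would not correct this sentence.
- *The numbers are approximate.* The SD units cannot be converted, the 0.30 s loss is illustrative, and once p-values are observed the interval is more informative than power. All of this stands. The power figures only show how far non-significance depends on sample size, and nothing here shows that a material loss is likely. The logical point needs none of these figures.
- *Attrition is acknowledged.* It is, and the loss is modest, but that caution concerns bias from missing people, not the reading of a non-significant test as evidence of no change.

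**Conclusion.** The concern holds. The claim of maintenance does not follow from the results given. As reported, the evidence is compatible with good maintenance and with a partial loss of benefit: losses of up to about 0.4 s (WSAS) and 0.5 s (ISI) remain open if the shift was a worsening, against about 0.2 s and 0.1 s if it was an improvement. These limits rest on the paired-t approximation, two-sided 5% tests and an effective sample of 39 to 46. The conclusion about the inference does not depend on them. The sentence should be corrected, but the defect is confined to the second aim and leaves the randomised between-arm comparison untouched.

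**What to change.** From the mixed model already fitted, report for the WSAS and the ISI the adjusted change from post-treatment to six months, its direction and its 95% confidence interval. Replace the maintenance claim with a statement that no significant change was detected and that durability was not established. If the interval excludes a loss margin that can be justified, a claim of maintenance can stand, with the margin given and labelled as post hoc, since the document contains none. A sensitivity analysis for the five people lost to follow-up would be a useful but optional addition.

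The cost is one reworded sentence and two estimates with intervals from existing output, with no new data. The downside for the sponsor is a possibly less favourable durability statement. If the intervals prove narrow and favourable, the claim becomes stronger.
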